All patients are planned to receive study drug during 6 months of treatment. The SEL-212 treatment arm will receive a total of up to 6 infusions, scheduled every 28 days. The KRYSTEXXA treatment arm will receive a total of up to 12 infusions, scheduled every 14 days, according to the manufacturer's currently approved label (*KRYSTEXXA Prescribing Information 2018*).

The total duration of participation in the study will range from approximately 26 to 31 weeks (184 to 219 days) for patients randomized to SEL-212 and approximately 28 to 33 weeks (198 to 233 days) for patients randomized to KRYSTEXXA as follows:

- Screening and/or washout and premedication period: up to 45 days (up to 6.5 weeks)
- Treatment: 168 days (24 weeks) for SEL-212 and KRYSTEXXA
- Safety Follow-Up: 30 (+ 4) days after the date of last infusion
 - SEL-212: Last scheduled infusion on Study Day 140
 - KRYSTEXXA: Last scheduled infusion on Study Day 154

Criteria for Evaluation:**Efficacy:****Primary Endpoint:**

- Comparison in the percentage of patients on SEL-212 vs. KRYSTEXXA who achieve and maintain reduction of SUA < 6 mg/dL for at least 80% of the time during Treatment Period 3 and Treatment Period 6

Secondary Endpoints:

- Comparison in the percentage of patients on SEL-212 vs. KRYSTEXXA who achieve and maintain reduction of SUA < 6 mg/dL for at least 80% of the time during Treatment Period 6

- Comparison in the percentage of patients on SEL-212 vs. KRYSTEXXA who achieve and maintain reduction of SUA < 6 mg/dL for 100% of the time during Treatment Period 6
- Comparison in the percentage of patients on SEL-212 vs. KRYSTEXXA who achieve and maintain reduction of SUA < 6 mg/dL for at least 80% of the time during Treatment Period 3
- Comparison in the percentage of patients on SEL-212 vs. KRYSTEXXA who achieve and maintain reduction of SUA < 6 mg/dL for 100% of the time during Treatment Period 3
- Comparison between patients on SEL-212 vs. KRYSTEXXA in pre-dose SUA values > 6 mg/dL during Treatment Periods 2-6. The pre-dose SUA is collected on the dosing day prior to the dosing administration or it is collected at the visit where dosing would have occurred had the patient not been previously withdrawn from study drug.
- Comparison between patients on SEL-212 vs. KRYSTEXXA of the change in health questionnaires
- Comparison between patients on SEL-212 vs. KRYSTEXXA of gout flare incidence per 3-month period (Treatment Periods 1-3 and Treatment Periods 4-6)

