7.1.2 Treatment Period

The total duration of treatment will be 6 months. Eligible patients will be randomized 1:1 prior to Baseline to receive SEL-212 or KRYSTEXXA.

Study patients in the SEL-212 arm will receive study drug every 28 days coinciding with Day 0 of each Treatment Period for a total of up to 6 infusions of SEL-212.

Study patients in the KRYSTEXXA arm will receive study drug according to the manufacturer's prescribing information, i.e., every 14 days coinciding with Day 0 and Day 14 of each Treatment Period for a total of up to 12 infusions of KRYSTEXXA.

Prior to infusion, all patients will receive a standardized regimen of premedication to minimize the potential for infusion reactions during study drug administration. After completing the study drug infusions, patients will remain at the investigational site for at least 1 hour for safety assessments.

Refer to [Section 10](#) for details about study drug administration.

With each dose, a blood sample will be drawn for assessment of SUA level immediately prior to infusion (ie, Time 0h) with SEL-212 or KRYSTEXXA, 1 hour after the infusion of the second component of SEL-212 or of KRYSTEXXA is completed. SUA levels will be assessed through additional post-infusion blood samples at pre-determined time points. Every effort will be made to obtain blood samples at the same time of day of each study visit.

[figure not shown]
Gout flares will be assessed at every visit. QoL and joint swelling and tenderness will be assessed on Day 0 of Treatment Period 1 and 4, and at the end of Treatment Period 6. Assessments of qualitative endpoints (health questionnaires and joint assessment) will be conducted on an assessor-blinded basis.

On dosing days, safety laboratory samples will be collected pre-infusion and per Schedule of Events in both the SEL-212 arm and the KRYSTEXXA arm. Concomitant medications and procedures and adverse events (AEs) will be monitored continuously during the study.

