7.7 Benefits and Risks

Chronic gout refractory to conventional therapy is a rare and serious condition associated with increased mortality rate and significantly decreased quality of life and for which there are very limited treatment options. Data from the Phase 2 study SEL-212/201 provide preliminary clinical evidence demonstrating that SEL-212 is a substantial improvement over available therapy:

- Substantially increased percentage of patients that maintain control of SUA while on therapy
- Substantially reduced gout flare rate during therapy
- Substantially reduced risk of infusion reactions
- More convenient to and greater compliance by patients because of once monthly therapy
- Acceptable safety at the doses to be studied in this Phase 2 study

SEL-212 has the potential to be an unprecedented safe and effective treatment option for patients for which other treatment options are inadequate. The overall balance between benefits and risks appears acceptable for the SEL-202/202 study of SEL-212 in the intended population of patients with chronic gout refractory to conventional therapy.

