12.2.1.5 Infusion Reactions / Adverse Events of Special Interest

A study drug-related AE that occurs within 24 hours after initiation of study drug infusion will be assessed as an infusion reaction. An infusion reaction suspected to be anaphylaxis will be assessed according to the clinical criteria for the diagnosis of anaphylaxis based on the National Institute of Allergy and Infectious Diseases (NIAID) / Food Allergy & Anaphylaxis Network (FAAN) Symposium criteria ([Sampson 2006](#)).

Infusion reactions will be managed and treated as described below. In addition to premedication with antihistamines and steroids ([Section 10.5.2](#)), the following steps will be implemented in this protocol to either reduce the risk of infusion reactions or manage infusion reactions.

- Patients with immunoreactivity to PEG will be ineligible for the study
- Patients with prior exposure to uricase therapy will be ineligible
- Patients with a history of anaphylaxis or severe allergic reactions, angioedema, or previous infusion reactions will be excluded from the trial.
- Study drug will be administered at controlled rates only in a healthcare setting and by healthcare providers sufficiently equipped and prepared to manage infusion reactions including anaphylaxis.
- In case of infusion reaction, sites will perform specific assessments as specified in the Study Operations Manual.
- Each patient will be observed for infusion reactions after dosing of study drug in the clinic for approximately 1 hour after the end of study drug infusion. Patients will be informed about the signs or symptoms of infusion reactions and will be instructed to notify the Investigator immediately if they believe they are experiencing a reaction.
- Each patient shall remain for a minimum of 1 hour after the completion of infusion of study drug for a period of safety observation.
- Only sites with immediate capability to appropriately respond to a reaction of this severity will be allowed to participate in the trial to reduce the risk to any patient.

Adverse events of special interest (AESI) will be recorded specifically for occurrences of: gout flares, infections, viral infections, interstitial lung disease, stomatitis, infusion-related reactions including anaphylaxis, malignancies, renal failure; and the following lab tests, if deemed

clinically significant by the PI: hyperlipidemia, worsening of renal function tests, proteinuria, and leukopenia.

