13.5 Safety Analyses

13.5.1 Extent of exposure:

Frequency counts of number of patients who received all doses (i.e., completed study treatment) and descriptive statistics of doses and total cumulative doses by treatment group (SEL-212 or KRYSTEXXA) will be presented.

13.5.2 Adverse Events / Adverse Drug Reactions:

All AEs will be coded and grouped into Preferred Terms (PT) by System Organ Class (SOC), using the most recent MedDRA Version. All AEs will be summarized by SOC and PT.

An overall summary will be provided of the number and percentage of patients reporting TEAEs, serious TEAEs, treatment-related TEAEs, AESIs, TEAEs leading to withdrawal, and TEAEs leading to death.

The number and percentage of patients with TEAEs / serious TEAEs / TEAEs leading to withdrawal/treatment-related TEAEs will be summarized by SOC and PT for each treatment group (SEL-212 or KRYSTEXXA). AESIs will also be summarized.

TEAEs will also be summarized by maximum intensity and causality.

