8.3. Adverse Events / Adverse Drug Reactions

All AEs will be coded and grouped into Preferred Terms (PT) by System Organ Class (SOC), using the most recent MedDRA Version. All AEs will be summarized by treatment, SOC and PT. A treatment-emergent AE (TEAE) is an AE that starts or worsens at any time after initiation of study drug on Day 0 of Treatment Period 1 until the End of Study Visit (30 days after completion of the last dose of study drug).

An overall summary will be provided of the number and percentage of patients reporting TEAEs, serious TEAEs, treatment-related (possibly related and related) TEAEs, Adverse events of special interest (AESIs), TEAEs leading to study drug withdrawal, and TEAEs leading to death. AESIs will be defined by medical monitor prior to database lock.

The number and percentage of patients with TEAEs / serious TEAEs / TEAEs leading to study drug withdrawal/treatment-related TEAEs will be summarized by SOC and PT for each treatment group (SEL-212 or KRYSTEXXA®). AESIs will also be summarized.

TEAEs will also be summarized by maximum intensity and causality.

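### Infusion reactions are reported only per patient, although planned dosing days are up to 6 on SEL-212 and up to 12 on KRYSTEXXA, so the table cannot describe risk per infusion

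*Protocol*

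**What the plan says.** **Definition.** Protocol 12.2.1.5: "A study drug-related AE that occurs within 24 hours after initiation of study drug infusion will be assessed as an infusion reaction". The same section lists "infusion-related reactions including anaphylaxis" among the AESIs. SAP 8.3 leaves the final AESI definition to the medical monitor before database lock; the protocol list is used here.

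**Dosing.** Protocol Synopsis: "The SEL-212 treatment arm will receive a total of up to 6 infusions, scheduled every 28 days", and "The KRYSTEXXA treatment arm will receive a total of up to 12 infusions, scheduled every 14 days". Protocol 7.4.1.1 and 7.4.1.2 set different serum uric acid (SUA) stopping rules for the two arms, so the infusions received can fall short of these maxima.

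**Reporting.** Protocol 13.5: "An overall summary will be provided of the number and percentage of patients reporting TEAEs, serious TEAEs, treatment-related TEAEs, AESIs". SAP 8.3 uses the same measure: "An overall summary will be provided of the number and percentage of patients". It adds only that AESIs will be summarised, without naming another denominator. SAP 8.1 summarises doses separately, and SAP 8.2 lists infusion start and stop times. Neither is used as a denominator for adverse events. SAP 6.1 has Kaplan-Meier curves for treatment discontinuation due to stopping rules or infusion-related reactions combined, which give no reaction rate.

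**Context.** Protocol 6.2.3 makes safety and tolerability compared with KRYSTEXXA an endpoint. Protocol 7.7 lists "Substantially reduced risk of infusion reactions" among the preliminary benefits seen in Phase 2.

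**The concern.** An infusion reaction can arise only after an infusion, and the comparator arm is planned to have up to twice as many occasions. A percentage of patients with at least one reaction rises with the number of infusions, even when each infusion carries the same risk. A lower SEL-212 percentage could therefore reflect fewer infusions, a less reactive product, or both, and the planned table cannot tell these apart.

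This matters because protocol 7.7 lists lower infusion-reaction risk separately from the convenience of monthly dosing, and protocol 5.6 links better safety to fewer anti-drug antibodies. A reader of the final table may take a lower percentage as support for that account.

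Person-time rates would not help. With full dosing, the treatment-emergent period ends about 140 + 30 = 170 days after first dose on SEL-212 and 154 + 30 = 184 days on KRYSTEXXA. Those are nearly equal, while planned dosing days differ 2:1.

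**Working it through.** The documents give no planned figure for this comparison, so there is none to reproduce. The responder assumptions borrowed in step 3 come from the sample-size section (protocol 13.1), whose 69 per group does reproduce (one-sided 5%, 80% power, 65% vs 44%, chi-square without continuity correction).

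**Inputs from the documents.** Up to 6 and up to 12 dosing days (Synopsis); 26% of KRYSTEXXA patients with infusion reactions and 6.5% with anaphylaxis (protocol 5.5); assumed responders 65% and 44% (protocol 13.1).

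**Assumptions.** The 26% and 6.5% apply over 12 infusions; per-infusion risk p is the same in both arms. Stop times and correlations below are illustrative, because the documents give none.

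**1. Number of occasions.** Each SEL-212 dosing day has two component infusions. The first takes 30 + 60 = 90 minutes and the second starts within 15 minutes of its end (protocol 10.6.1), so the two 24-hour windows overlap almost fully (at most about 25.75 h in total). Distinct occasions stay at 6 vs 12.

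**2. Full dosing, constant independent risk.** P(at least one reaction in m infusions) = 1 − (1 − p)^m.
- Infusion reactions: p = 1 − (1 − 0.26)^(1/12) = 0.0248. Over 6 infusions: 1 − (1 − 0.0248)^6 = 0.140. Ratio 0.140/0.26 = 0.54.
- Anaphylaxis: p = 1 − (1 − 0.065)^(1/12) = 0.0056. Over 6 infusions: 0.033. Ratio 0.51.
- Other values of p: ratio 0.51 at 0.5%, 0.52 at 1%, 0.58 at 5%, 0.65 at 10%.

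**3. Early stopping.** Take the responder rates as the share receiving all doses (a proxy). The rest stop after k KRYSTEXXA or s SEL-212 doses. Mean infusions are 0.44×12 + 0.56×k and 0.65×6 + 0.35×s. The patient percentage is the same weighted mix of the step 2 formula.

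| k, s | Mean infusions (KRYSTEXXA vs SEL-212) | Infusion ratio | Patient-percentage ratio, p = 1% to 5% |
|---|---|---|---|
| 2, 1 | 6.40 vs 4.25 | 1.5 | 0.68 to 0.74 |
| 4, 2 | 7.52 vs 4.60 | 1.6 | 0.63 to 0.67 |
| 6, 3 | 8.64 vs 4.95 | 1.7 | 0.59 to 0.63 |
| 8, 4 | 9.76 vs 5.30 | 1.8 | 0.56 to 0.61 |

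Worked cell (k = 2, s = 1, p = 2.5%): KRYSTEXXA 0.44×0.262 + 0.56×0.049 = 0.143; SEL-212 0.65×0.141 + 0.35×0.025 = 0.100; ratio 0.70. If the stopped share and relative timing were equal in both arms, the 2:1 infusion ratio would remain.

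**4. Clustering within patients, full dosing.** Beta-binomial with mean per-infusion risk 2.5%:
- Correlation 0.01: 13.8% vs 25.0%, ratio 0.55.
- Correlation 0.10: 11.4% vs 18.1%, ratio 0.63.
- Correlation 0.30: 8.1% vs 11.1%, ratio 0.73.

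Steps 3 and 4 were varied one at a time. Their combination was not worked out, so 0.74 is not a bound.

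**The case against.** The strongest reply is that the percentage of patients is the normal safety measure for comparing two regimens. Fewer infusions is a real feature of SEL-212. No test of infusion-reaction incidence is planned, and protocol 7.7 does not claim lower risk per infusion. All of that stands: the planned table is correct for what it measures, and the gap is only that nothing beside it speaks to risk per infusion.

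Three stronger readings are tempting, and the documents do not support them.

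- **That equal risk would show as half the rate.** This needs full dosing in both arms, low risk and independent reactions. Protocol 5.5 says that reactions track antibody titre and usually follow loss of urate lowering, so they probably cluster in some patients, and the SUA stopping rules tend to end dosing in those same patients. Both move the ratio towards 1. Nor do the documents say that the 26% was observed over 12 infusions or under this trial's premedication and stopping rules.
- **That the 24-hour window causes the imbalance by doubling the hours at risk.** The event must also be judged drug-related, so the label does not simply collect background events. More infusions give more true reactions whatever the window length.
- **That a per-infusion table would show whether tolerance induction works.** It would not. The arms differ in enzyme, schedule and stopping rule, and no arm receives the SEL-212 uricase alone. Infusions received also depend on what happens after randomisation, so the per-infusion contrast is itself selected.

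**Conclusion.** The point holds as a reporting gap, not as an invalid analysis. The per-patient percentage is a sound regimen-level result, but alone it cannot support a statement about reaction risk per infusion. With equal per-infusion risk, the ratio of patient percentages would be about 0.54 under full dosing and constant independent risk, anchored on the protocol's 26% over an assumed 12 infusions. It would be about 0.55 to 0.74 under the assumed early stopping or clustering. In every scenario tried, the apparent advantage goes to SEL-212. The direction follows from the dosing schedules; the size depends on stop times and correlations that the documents do not give.

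**What to change.** In SAP 8.3:

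1. Keep the per-patient table and label it as the regimen-level result.
2. Add a supportive table of dosing days with an infusion reaction, and separately with anaphylaxis, divided by dosing days started. Show it by arm, overall and by dosing-day number, counting the two SEL-212 components as one dosing day. Give a patient-clustered interval for the arm difference, for example from a GEE logistic model.
3. State how reactions that start outside the clinic are linked to the 24-hour window. Protocol 12.2.2 requires the clock time of an event only while the patient is in the clinic.
4. State that the per-infusion result is descriptive and conditional on continued dosing, and is not the sole basis for a product claim.

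The cost is SAP wording and one table. Infusion start and stop times are already recorded (protocol 9.3, SAP 8.2), although some reactions after discharge may lack an onset time. The per-infusion contrast may be less favourable to SEL-212 than the per-patient one.

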12.2.2 Recording Adverse Events

Patients will be encouraged to spontaneously report any changes in health from the time of signing the ICF through completion of the study. Study staff will also inquire about any changes in the patient's health.

All AEs will be recorded in the source document and the CRF. It is the responsibility of the Investigator to review all documentation (e.g., hospital progress notes, laboratory, and diagnostics reports) for the presence of AEs and for a complete evaluation of known AEs.

At minimum for each AE, the Investigator will evaluate and report the event name/term/description, onset (date and time), resolution (date and time), event severity/intensity, relationship to study drug, action taken in regard to study drug, whether the event is an SAE, and whether or not it caused the patient to discontinue the study. The event time is only required while the patient is in the clinic.

During the Screening Phase (from time informed consent is signed to immediately before dosing) any clinically significant changes in the patient's health will be recorded in the patient's medical history and will not be considered as AEs.

12.2.2.1 Adverse Event Term/Name/Description

The Investigator will attempt to establish a diagnosis of each AE based on signs, symptoms, and/or other clinical information. In such cases, the diagnosis will be the AE term used to document the AE/SAE and not the individual signs/symptoms.

12.2.2.2 Relationship to Study Drug

The Investigator is obligated to assess the relationship between study drug and the occurrence of each AE. The Investigator will use clinical judgment to determine the relationship. Alternative causes, such as natural history of the underlying diseases, concomitant therapy, other risk factors, and the temporal relationship of the event to the study drug will be considered and investigated. The Investigator will also consult the SEL-212 Investigator's Brochure and/or Product Information for marketed products in the determination of his/her assessment.

The Investigator will assess causality as to whether the event is related or not related to study drug based on the following definitions:

- Not Related: If no valid reason exists for suggesting a relationship to study drug or the AE was more likely explained by causes other than study drug.
- Unlikely to be Related: Onset of the event has a reasonable temporal relationship to study drug administration and although a causal relationship is unlikely, it is biologically plausible.

- Possibly Related: Onset of the event has a strong temporal relationship to administration of the study drug and a causal relationship is biologically plausible
- Related: The study drug dosing and AE were closely related in time and the AE may be explained by exposure to study product: e.g., known pharmacological effect or recurrence on re-challenge.

There may be situations, particularly when an SAE has occurred, where the Investigator has minimal information to make an assessment in an initial SAE report. However, it is very important that the Investigator always makes an assessment of causality for every SAE prior to transmission of the SAE report. The Investigator may change his/her opinion of causality in light of follow-up information, amending the SAE report accordingly. Any assessment of causality made by the Investigator should also be documented in the patient's source medical record.

12.2.2.3 Adverse Event Intensity/Severity Grading

AEs will be classified according to the Rheumatology Common Toxicity Criteria, version 2.0 ([Woodworth 2007](#)). Additional details of the criteria can be found in the study operations manual.

- Grade 1 (mild): AE that is usually transient of short duration; or involves mild or minor symptoms which are of marginal clinical relevance; or is asymptomatic consisting of clinical or diagnostic observations alone; no intervention or only minimal treatment with non-prescription intervention was required. The event does not generally interfere with usual activities of daily living.
- Grade 2 (moderate): AE that is usually alleviated with additional specific therapeutic intervention. The event interferes with usual activities of daily living (e.g., shopping, laundry, transportation, or ability to conduct finances), causing discomfort but poses no significant or permanent risk or harm to the patient.
- Grade 3 (severe): AE that is medically significant/important but not life-threatening; may require brief hospitalization to prevent the event from worsening; interrupts usual activities of daily living, or significantly affects clinical status, or may require intensive therapeutic intervention.
- Grade 4 (life-threatening): An AE, and/or its immediate sequelae, which is associated with an imminent risk of death or which is associated with physical or mental disabilities that affect or limit the ability of a person to perform activities of daily living (eating, ambulation, toileting, etc.); disability may be persistent or result in significant disability, incapacity or limitation of self-care activities.

For an assessment of anaphylaxis, the clinical criteria for the diagnosis of anaphylaxis will be based on the NIAID/FAAN Symposium criteria ([Sampson 2006](#)).

